7.6. Bone Age

Observed and change from baseline in bone age will be listed and summarized by visit using descriptive statistics. Bone age will be summarized as "chronological age" and "bone age" as reported as XR report.

7.7. Seizure Count

Observed seizure counts will be listed and summarized by visit using descriptive statistics, for both the overall seizure count and by seizure type (Partial, Partial Evolving into Secondary Generalized, Primary Generalized Tonic-Clonic, and Other).

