Physical activity evaluation ^f	X								
Prestudy AED and other therapy ^g	X								
Randomization		X							
Study Drug									
Dispense study drug		X	X	X	X	X	X		
Study drug accountability			X	X	X	X	X	X	
Pharmacokinetics									
Blood sample collection for quantitation of study drug ^h			X		X	X		X	
Safety									
Physical examination	X	X	X		X	X	X	X	
Neurologic examination	X	X	X		X	X	X	X	
12-lead ECG	X								
Height/weight ⁱ	X	X	X		X	X	X	X	
Vital signs (temperature, HR, RR, BP) ^j	X	X	X		X	X	X	X	
Clinical laboratory tests ^k	X		X		X	X	X	X	
Pregnancy test ^l	X	X	X	X	X	X	X	X	
24-hour urine collection ^m	X					X		X	
Tanner staging ⁿ		X				X		X	

Phase	Screening	Open-Label Treatment ^a						Posttreatment ^b	
		Baseline/ W1	M1	M2	M3	M6	M9	End-of- Study/Early Withdrawal	Follow-up Telephone Contact
Week (W)/Month (M)									
Study Day	≤-28	1 ^c	30	60	90	180	270	360	390 ^d
Study Day Window	-7days	±7days	±7days	±7days	±7days	±7days	±7days	±7days	±7days
Visit ^e	1	2	3	4	5	6	7	8	NA
Renal ultrasound ^o	X					X		X	
Biochemical bone markers ^p	X					X		X	
DEXA scan ^{b,q}		X				X		X	
Bone age x-ray ^f		X						X	
Dispense seizure diary and take-home record ^s		X	X	X	X	X	X		
Review seizure diary and take-home record			X	X	X	X	X	X	
Cogstate Battery ^t	X	X				X		X	
Animal Fluency Test NEPSY-II ^u	X	X				X		X	
Vineland Adaptive Behavior Scale ^v		X			X	X		X	
CBCL-Parent Version ^w		X			X	X		X	
C-SSRS ^x		X	X	X	X	X	X	X	
Ongoing Review									
Concomitant therapy	X	X	X	X	X	X	X	X	X
Adverse event monitoring	X	X	X	X	X	X	X	X	X

Footnotes appear on the following page.

^a Includes a titration period of approximately 6 to 8 weeks, followed by a maintenance period.

^b There may be an optional post-study follow-up phase to obtain DEXA measurements in a subgroup of subjects who experience a clinically important reduction (change in Z-score of -0.5 or greater) in BMD, based on local DEXA scan results, after 1 year of treatment with topiramate; these subjects will have a repeat DEXA scan 6 months after discontinuation of study drug.

^c The Day 1 visit will serve as the baseline visit. All procedures on Day 1 (except dispensing of study drug) should be completed before randomization.

^d The site will contact the subject via telephone at Month 13, to collect data on adverse events and concomitant medications.

^e Window for all visits will be ±7 days.

^f Adequacy of physical activity will be assessed with the Habitual Activity Estimation Scale.

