Only AED monotherapy will be used for both treatment groups. However, subjects will not be discontinued from the study if 1 or more concomitant AEDs are added after initiating treatment with study drug. Data will be collected prior to the use of the concomitant AED(s) for the primary analysis. Data subsequently collected while on the concomitant AED(s) will be analyzed in a secondary analysis for each safety outcome of interest.

All subjects will enter a 30-day posttreatment phase after completing the open-label treatment phase.

The open-label treatment phase has 2 periods, titration and maintenance.

Titration Period

Randomization will take place on Day 1 (Visit 2). The Day 1 visit will serve as the baseline visit. All procedures on Day 1 (except dispensing of study drug) should be completed before randomization.

Study drug will be titrated as tolerated to the maximum recommended dosage for optimal clinical effect over approximately 6 to 8 weeks, based on titration guidelines according to clinical response (see Section 6, Dosage and Administration). For all subjects, at any time, up-titration of open-label study drug may be slowed down if clinically indicated for tolerability, and may be accelerated if clinically indicated for seizure control.

Subjects will return for a clinic visit at Month 1 and Month 2 for dispensing of study medication.

Maintenance Period

Subjects should be maintained on the dosage achieved at the end of the titration period through the remainder of the open-label treatment phase, with the option for dosage adjustment as required for optimal clinical effect. Changes to this schedule will be based on a risk-benefit assessment of the subject's clinical condition by the investigator.

Clinic visits will be scheduled at Months 1, 2, 3, 6, 9, and 12/early withdrawal. Extra visits may be scheduled at the discretion of the investigator. Blood samples for PK evaluations will be taken at Months 1, 3, 6, and 12/early withdrawal.

Posttreatment Phase

[figure not shown]
Subjects will be contacted by telephone 30 days after the last dose of study drug to monitor adverse events and concomitant medications. Subjects who complete the study or discontinue early from the study may, at the discretion of the investigator, either continue on commercially available topiramate or levetiracetam or taper off topiramate or levetiracetam over a period of up to 2 weeks during the posttreatment phase.

Post-Study Follow-up Phase

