9.1.3. Open-Label Treatment Phase

The open-label treatment phase includes randomization and distribution of study drug and titration instructions (Visit 2; Day 1), a 6- to 8-week titration period, and a maintenance period, during which subjects will remain in the study until they either complete 1 year of open-label treatment or withdraw from the study.

Subject take-home records and seizure diaries will be given to parents/guardians at Visit 1 and at each subsequent visit. Each subject's parent will record in the seizure diary the date, description, and number of seizures. The investigator or designated study personnel will review the data to be recorded in the subject take-home record with the subject's parents/legally acceptable representatives at the beginning of the study. At each visit, the investigator will review the seizure data, and then transcribe the data onto the appropriate page of the CRF.

Titration intervals and dosages may be adjusted for individual subjects to achieve their optimal dosage. Subjects receiving 1 concomitant AED at baseline for any purpose will have their AED tapered down and discontinued in one-third decrements during the 6- to 8-week titration period.

At the end of the titration period, the dosage of study drug should be maintained but may be adjusted at the investigator's discretion for optimal clinical effect.

Subjects will return for a clinic visit at Months 2 and 3, with subsequent visits to occur every 3 months.

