3.1. Visit Windows

The statistical analysis for safety will be based on time intervals that are constructed according to the number of days in trial from day 1. (See table 2-8)

The analysis windows for height, weight, exposure, vital signs, laboratory tests, physical examination and neurological examinations is given in [Table 2](#).

Table 2: Definition of windows for height, weight, exposure, vital signs, laboratory tests, physical examination and neurological examinations:

Scheduled Visit Number	Time Interval (label on output)	Time Interval (Day) ^a	Target Time Point
1,2	Baseline	-35 to 1	1
3	Month 1	2 to 60	30
5	Month 3	61 to 135	90
6	Month 6	136 to 225	180
7	Month 9	226 to 315	270
8	Month 12	≥ 316	360

^a The randomization day is Day 1.

The analysis windows for Renal Ultrasound, Cogstate, Tanner Staging and 24 hour urine collection is given in [Table 3](#).

Table 3: Definition of windows for Renal Ultrasound, Cogstate, Tanner Staging and 24 hour urine collection:

Scheduled Visit Number	Time Interval (label on output)	Time Interval (Day) ^a	Target Time Point
1, 2	Baseline	-35 to 1	1
6	Month 6	2 to 270	180
8	Month 12	≥ 271	360

^a The randomization day is Day 1.

The analysis windows for C-SSRS is given in [Table 4](#).

Table 4: Definition of windows for C-SSRS:

Scheduled Visit Number	Time Interval (label on output)	Time Interval (Day) ^a	Target Time Point
1, 2	Baseline	-35 to 1	1
3	Month 1	2 to 45	30
4	Month 2	46 to 75	60
5	Month 3	76 to 135	90
6	Month 6	136 to 225	180
7	Month 9	226 to 315	270
8	Month 12	>=316	360

^a The randomization day is Day 1.

The analysis windows for Vineland Scale and CBCL is given in [Table 5](#).

Table 5: Definition of windows for Vineland Scale and CBCL:

Scheduled Visit Number	Time Interval (label on output)	Time Interval (Day) ^a	Target Time Point
1, 2	Baseline	-35 to 1	1
5	Month 3	2 to 135	90
6	Month 6	136 to 270	180
8	Month 12	>=271	360

^a The randomization day is Day 1.

The analysis windows for Bone Age is given in [Table 6](#).

Table 6: Definition of windows for Bone age:

Scheduled Visit Number	Time Interval (label on output)	Time Interval (Day) ^a	Target Time Point
1	Baseline	-35 to 180	1
8	Month 12	>=181	360

^a The randomization day is Day 1.

The analysis windows for seizure count is given in [Table 7](#).

Table 7: Definition of windows for seizure count:

Scheduled Visit Number	Time Interval (label on output)	Time Interval (Day) ^a	Target Time Point
3	Month 1	2 to 45	30
4	Month 2	46 to 75	60

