5	Month 3	76 to 135	90
6	Month 6	136 to 225	180
7	Month 9	226 to 315	270
8	Month 12	>=316	360

^a The randomization day is Day 1.

The analysis windows for DEXA is given in [Table 8](#).

Table 8: Definition of windows for DEXA:

Scheduled Visit Number	Time Interval (label on output)	Time Interval (Day) ^a	Target Time Point
1, 2	Baseline	-35 to 30	1
6	Month 6	31 to 270	180
8	Month 12	>=271	360

^a The randomization day is Day 1.

The analysis windows for Pharmacokinetics is given in [Table 9](#).

Table 9: Definition of windows for Pharmacokinetics

Scheduled Visit Number	Time Interval (label on output)	Time Interval (Day) ^a	Target Time Point
3	Month 1	2 to 45	30
5	Month 3	46 to 135	90
6	Month 6	136 to 270	180
8	Month 12	>=271	360

^a: The randomization day is Day 1

Baseline is defined as the last non-missing observation (including an unscheduled visit) prior to or equal to Day 1 (except for DEXA and Bone age, where baseline includes up to 30 days and 180 days post-baseline, respectively).

For post baseline observations, if more than one visit (including an unscheduled visit) occurs in the same time window, the visit nearest to the target day will be used in the analysis. In the case of an equal distance in time, the latest visit will be used.

Data that are not used in the analysis due to multiple observations or being excluded from the above defined time intervals will be displayed in the data listing.

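### Seizure counts are tabulated by visit with no allowance for observation time, and a record-selection rule meant for point measurements is applied to them

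*SAP*

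**What the plan says.** SAP 7.7 is a single sentence: "Observed seizure counts will be listed and summarized by visit using descriptive statistics, for both the overall seizure count and by seizure type", followed by the list of types. It defines no rate, no denominator and no reference period. Protocol 11.4 adds only that counts are summarised by treatment group and age group.

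On timing, Protocol 3.1 (Maintenance Period) says: "Clinic visits will be scheduled at Months 1, 2, 3, 6, 9, and 12/early withdrawal". The same paragraph lets the investigator add visits. Protocol 9.1.3 gives the change of spacing: "Subjects will return for a clinic visit at Months 2 and 3, with subsequent visits to occur every 3 months". The Time and Events Schedule places these visits on Days 30, 60, 90, 180, 270 and 360, and its footnote e adds: "Window for all visits will be ±7 days".

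SAP 3.1 gives seizure counts their own day windows in Table 7. For all post-baseline observations it then says that "if more than one visit (including an unscheduled visit) occurs in the same time window, the visit nearest to the target day will be used", with ties going to the later visit. It makes no exception for counts. Records not used for this reason go to the data listing.

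Under Protocol 9.1.3, parents enter the date, description and number of seizures in a diary, and the investigator reviews the entries at each visit and transcribes them to the CRF. Neither document says whether the analysed count runs since the previous visit or is rebuilt from the dates.

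**The concern.** A seizure count accumulates over time, so it means something only together with the length of time it covers. Here that length changes by design partway through the year, and the summary ignores it. A reader comparing Month 3 with Month 6 could take a change of schedule for a loss of seizure control.

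The nearest-visit rule adds a second problem. For height or a laboratory value, choosing the visit closest to the target day selects a representative reading. For a count since the last visit, discarding a record discards observation time and the seizures in it, and the record that is kept may cover only part of the interval its label suggests.

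At stake is the SAP's direct summary of seizure control. It gives context for the growth and bone results, because Protocol 8 links insufficient seizure control to add-on AEDs, and the start of an add-on AED defines the sensitivity analysis for height, weight and BMD Z-scores in SAP 7. The SAP already handles this kind of problem elsewhere: Appendix 6 divides height change by the actual interval between measurements.

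**Working it through.** The documents give no expected seizure count, so there is no figure to reproduce. The check is direct arithmetic on the schedule and on the Table 7 windows.

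**Step 1. Time behind each count.** Since-last-visit days are the differences between Days 1, 30, 60, 90, 180, 270 and 360. By-date days are the last day minus the first day plus 1 in each Table 7 window. Month 12 is open-ended, so it is cut here at Day 360 (52 days if cut at Day 367).

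| Visit | Table 7 window | Days since last visit | Days by date |
|---|---|---|---|
| Month 1 | 2–45 | 29 | 44 |
| Month 2 | 46–75 | 30 | 30 |
| Month 3 | 76–135 | 30 | 60 |
| Month 6 | 136–225 | 90 | 90 |
| Month 9 | 226–315 | 90 | 90 |
| Month 12 | ≥316 | 90 | 45 |

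Both columns sum to 359 days.

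**Step 2. Apparent change at a constant rate.** Expected count = rate × days, so the ratio of two visits equals the ratio of their days, whatever the rate.

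- Since last visit, Month 6 to Month 3: 90/30 = 3.0. At the extremes of the ±7-day tolerance: (90 − 14)/(30 + 14) = 1.7 and (90 + 14)/(30 − 14) = 6.5.
- By date, Month 6 to Month 3: 90/60 = 1.5. The other steps are uneven too: Month 3 to Month 2 is 60/30 = 2.0, and Month 12 to Month 9 is 45/90 = 0.5.

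For scale, Protocol 4.1 admits 1 to 10 seizures in 5 months, or 0.2 to 2 per month. No on-treatment rate is given. Taking that range as an assumption, with a month as 30 days, since-last-visit counts at Months 2, 3, 6, 9 and 12 run 0.2, 0.2, 0.6, 0.6, 0.6 at the low end and 2, 2, 6, 6, 6 at the high end.

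**Step 3. Nearest-visit rule, since-last-visit reading only.** All scheduled visits are taken as on target.

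- Extra visit on Day 120: it falls in the Month 3 window and loses to Day 90. Its 30 days drop out, the Month 6 count covers 180 − 120 = 60 of 90 days, and 329 of 359 days are summarised.
- Extra visit on Day 150: it falls in the Month 6 window and loses to Day 180. Its 60 days drop out, the Month 6 count covers 30 of 90 days, and 299 of 359 days are summarised.
- One extra visit on any non-scheduled day from 91 to 359 drops 1 to 89 days, 45 on average.
- Two extra visits in each 90-day gap (Days 120, 150, 210, 240, 300, 330) leave 179 of 359 days, or 50%.

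**Step 4. Early-withdrawal visits.** After an on-target visit, a withdrawal visit on Days 91–135, 181–225 or 271–315 falls in a window already filled by Day 90, 180 or 270, so its count leaves the summary. Each range is 45 days, half of its 90-day gap. A withdrawal on Day 140 is kept, but puts a 140 − 90 = 50-day count into a cell of 90-day counts.

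**Step 5. Check of the remedy.** Dividing each count by its own days returns the same rate at every visit under either reading. Assigning by date with no record dropped uses 44 + 30 + 60 + 90 + 90 + 45 = 359 of 359 days.

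**The case against.** A reader might infer that breakthrough seizures are deleted, that counts certainly triple, and that the arm with more seizure-driven visits is made to look better. The documents do not support any of these as stated.

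- **Nothing is deleted.** SAP 3.1 sends unused records to the listing, and SAP 7.7 lists the counts. Worsening can also appear in adverse events (Protocol 12.1.1), discontinuation reasons (SAP 5.2) and concomitant AEDs (SAP 5.6). This stands, although a listing does not correct a summary table.
- **The factor of 3 and the excluded records depend on an unstated reference period.** Diaries are dated and Table 7 is defined in days. If seizures are assigned by date, the nearest-visit rule has nothing to discard and the Month 3 to Month 6 step is 1.5. This stands, but the table remains not comparable over time under that reading too.
- **Between-arm bias is not shown.** Both arms follow the same schedule, so unequal intervals distort the time trend rather than the comparison at a given visit. A bias would need extra visits or withdrawals that are related to seizures and differ by arm. The documents leave extra visits to the investigator and give neither numbers nor reasons. Some grounds for withdrawal in Protocol 10.2 are seizure-related and seizure frequencies are reviewed at that visit (Protocol 9.1.4), so an informative loss is plausible, but no more than that.
- **The variable is minor.** Seizure counts are not among the key safety endpoints in Protocol 11.4, SAP 7 plans no formal testing, and no growth or bone model contains them. This stands and limits the weight of the point.

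**Conclusion.** The point holds in a limited form. Whichever way the count is built, the by-visit table in SAP 7.7 is not comparable over time. The Month 3 to Month 6 step at a constant rate is about 3 times under the since-last-visit reading (1.7 to 6.5 within the visit tolerance) and about 1.5 times by date.

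The exclusion of counts by the nearest-visit rule is conditional on the since-last-visit reading. It then affects extra visits, and withdrawal visits in half of each 90-day gap when the preceding visit was on target. Its actual size is unknown, because the number of extra visits is not given and the 29% dropout in SAP 2.4 is a planning assumption with no timing attached.

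This is more than missing detail: a stated rule gives a wrong summary when it is applied to this type of data. It is worth correcting, but it does not touch the key endpoints.

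**What to change.** In SAP 7.7, state the reference period. Assign each seizure to its Table 7 interval by diary date, using all scheduled and unscheduled records. Divide by the child's days on study in that interval, or by days with diary coverage where these are recorded. Report a rate per 28 or 30 days, by interval and over the whole treatment phase. In SAP 3.1, state that the nearest-visit rule does not apply to seizure counts.

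Assignment by date is needed, because adding up visit records within a window is not enough. Even the routine Day 180 record covers Days 91–180, and 45 of those days (91–135) belong to the Month 3 window.

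The cost is a few sentences and modest extra programming for a descriptive variable. The seizure dates are already in the diary. The documents do not say that diary completeness is recorded day by day. If it is not, the denominator has to be days on study, and the rate will be too low where diaries have gaps; the table should carry a note to that effect.

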7.8. Cognitive, Developmental, and Behavioral Assessments

Cognitive Assessments

For the cognitive assessments (Detection Test, Identification Test, One Card Learning Test, One Back Test, and Groton Maze Learning Test) the standardized observed scores and change from baseline in standardized scores will be listed and summarized by visit using descriptive statistics. The standardized scores will be calculated by setting the observed raw score in relation to the expected within-subject standard deviations for each Cogstate task (see table 1-5 of [Appendix 1](#) for normative data). For the tasks which lower scores indicate improvement (e.g., Detection Test and Identification Test), the score will be multiplied by (-1), so that a negative change in standardized scores represent a decline in cognitive performance consistently across all tasks.

A meaningful decline in cognition has been defined as a change in standardized score of less than -1.65 from the baseline standardized score. These calculations will indicate meaningful decline at the subject level. Each individual change in standardized scores that meet the definition of a meaningful decline will be identified using a binary flag, where 1 represents a meaningful decline from baseline and 0 otherwise. The number and percentage of subjects with a meaningful decline in cognition will be listed and summarized by visit.

Cognitive assessments will be provided to subjects of 4 years and older. Cognitive data collected after a subject turn 16 will not be included in the analysis.

For example, if a 10-year-old female subject has an observed raw score at baseline of 1.2 for the detection test, then the standardized score will be $1.2/0.0882*(-1)=-13.605$. For a post baseline visit the subject had an observed raw score of 1.0, which is a standardized score of -11.338. The

change from baseline would be 2.267. The lower score at post baseline indicates an improvement in Detection Test which is reflected by the positive change (see table 1 of [Appendix 1](#)).

Developmental Assessments

The Vineland Scales of Adaptive Behavior provide age-specific assessment of function in the domains of communication, daily living, socialization, and motor skills, as well as a composite scale. The subject's sub-domain raw scores are entered on the CRF. The derived domain scores (standardized scores) based on the national standardization sample must be obtained from these raw scores. The derived scores are used in the analyses. The Vineland standardized scores for domain scores have a mean of 100 and a standard deviation of 15.

The composite score will be the sum of 4 standardized domain scores. If a subject has only 3 domains, then the standardized score for the missing domain will be prorated and the composite score will be calculated as sum of 4 domains. If a subject has less than 3 domains, then the composite score will not be calculated.

The standardized scores and the changes in standardized scores from baseline will be listed and summarized by visit using descriptive statistics.

For manuals and SAS program calculating the standardized domain scores, please see [Appendix 4](#).

The Vineland Adaptive Behavior Scale will be administered for subjects 2 to 5 years of age only.

Behavioral Assessments

For CBCL preschool (up to 5 years of age), a raw total score will be sum of 99 non-missing answers (range of 0-198).

For CBCL school age (6 to 18 years of age), a raw total score will be the sum of 112 non-missing answers (range of 0-224).

The domains will be:

CBCL preschool	CBCL school age
1. Emotionally Reactive	11. Anxious/depressed
2. Anxious/Depressed	12. Withdrawn/depressed
3. Somatic Complaints	13. Somatic complaints
4. Withdrawn	14. Social problems
5. Sleep Problems	15. Thought problems
6. Attention Problems	16. Attention problems
7. Aggressive Behavior	17. Rule breaking behavior
8. Internalizing Problems	18. Aggressive behavior
9. Externalizing Problems	19. Internalizing Problems
10. Total Problems	20. Externalizing Problems
	21. Total Problems

The standardized total scores (T score) for all domains will be derived using the charts based on the raw scores ([Appendix 5](#)).

The standardized scores and the changes in standardized scores from baseline will be listed and summarized by visit using descriptive statistics.

